#### Primary Safety Outcome:

- Hematoma formation: small ranging from small <5cm [I], 5-10cm [II] , or large >10cm. Hematoma assessment will be done in multiple incidences: at the time of Perclose deployment while in the catheterization lab, at the time of admission to the recovery unit by the TAVR team, and at the time of admission to the inpatient service for overnight monitoring. While in recovery the patient will be evaluated by the staff for 15 minutes for one hour, every 30 minutes for the next hour, and every hour for the subsequent four hours (for a total of 6 hours post-procedure while in the recovery unit). While admitted for overnight monitoring (at least for a 24 hour period), the patient will have their site evaluated every 4 hours until the 24 hours period has been reached.

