### **III. STUDY OBJECTIVE(S)**

The primary objectives of this study are to evaluate the performance of StatSeal Advanced used in conjunction with the Perclose™ (SS) as compared to the Perclose™ without SS (PC) relative to:

TAVR Outcomes:

1. Primary outcome: Time to Hemostasis (TTH)
2. Secondary outcome: The incidence of access hematomas

Time to hemostasis (TTH) is defined as the time period required to achieve hemostasis, beginning at the time at which the Perclose™ is deployed to the access site to when no additional bleeding is appreciated..

Hematoma are defined as being <5 cm, 5-10 cm, and >10 cm. The physician on the study team will make the assessment for the incidence and size of the hematoma based on physical exam and /or diagnostic imaging including ultrasound. Hematoma assessment will be done in multiple incidences: at the time of Perclose deployment while in the catheterization lab, at the time of admission to the recovery unit by the TAVR team, and at the time of admission to the inpatient service for overnight monitoring. While in recovery the patient will be evaluated by the staff for 15 minutes for one hour, every 30 minutes for the next hour, and every hour for the subsequent four hours (for a total of 6 hours post-procedure while in the recovery unit). While admitted for overnight monitoring (at least for a 24 hour period), the patient will have their site evaluated every 4 hours until the 24 hours period has been reached.

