#### **STUDY METHODS:**

Patient Selection Criteria Study subjects will be identified in their outpatient appointments during their appointments with the structural heart team prior to their TAVR procedure.

Inclusion Criteria:

- Left heart catheterization with plans for delivery of a 14-16 Fr TAVR system

Exclusion Criteria:

Candidates for this study will be excluded if any **one** of the following criteria is true.

- Use of a hemostasis method or device besides Perclose™ (Perclose may not be used in situations of heavy calcification, presence of dissection, etc).
- Use of an anticoagulant other than unfractionated heparin or bivalirudin during the procedure.
- Any use of glycoprotein inhibitors or cangrelor.
- Use of sheathless guides.
- Any anticipated need for continued anticoagulation post-catheterization, including extended bivalirudin infusion.
- Any active treatment with oral anticoagulants continued during course of procedure.
- Presence of arteriovenous dialysis fistula in the ipsilateral leg.
- Any physical deformity or trauma / injury of the leg that would prevent proper placement or function of the hemostasis band.
- Inability of the patient to personally consent for the study. (no surrogate consent)
- Cardiogenic shock, emergent procedures (high risk myocardial infarctions), or any clinical instability as assessed by the physician performing the procedure.

Transfemoral Catheterization Procedure

TFA Cardiac Catheterization will be performed according to local practice standards with use of a 14-16 Fr sheath during a TAVR procedure.

Patients will have their activated clotting time measured prior to sheath removal and at least 5 minutes following the initial dose of anticoagulant. Additional activated clotting time measurements for PCI would be expected as part of routine practice but not recorded. Vasodilators (nitroglycerin, verapamil) will be administered in accordance with local practice.

Timing of Subject Enrollment

A subject will be consented into the study prior to the administration of sedation prior to the procedure, and randomized at the conclusion of a successful deployment of the Perclose device (after all anticoagulation and antiplatelet medication decisions have been made), at which time placement of the assigned device will occur. Eligibility for the study will be assessed at this time and the subject will have to meet all of the inclusion criteria and none of the exclusion criteria.

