Randomization will be performed by means of sealed envelopes in randomization blocks of 25. Each envelope will be labeled by patient number containing device designation. Device designation in the envelopes will be random in occurrence. When a patient is officially enrolled (after Perclose™ deployment) the envelope corresponding to that patient number in the Study Patient log will be pulled, opened, and the assignment revealed.

End of Study Status / Effect of Withdrawals:

A subject will have completed the study when one of the following events is documented:

1. The patient is successfully enrolled, treated with a Perclose™, and completes all required follow up.

2. A subject withdraws consent to participate. Patients who withdraw from the study will have their data included to the extent allowable by law. As all study related procedures are expected to be completed on the day of the procedure or day after, subject withdrawal is not considered likely.

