### **VI. STUDY STATISTICAL PLAN:**

This is a physician initiated, prospective, randomized, two-arm study, to be conducted at high-

volume academically affiliated centers with the cath lab staff having a (minimum) ten case experience using StatSeal Advanced. The primary analysis will be by intention-to-treat methodology.

A sample size of 50 patients is sufficient to have >90% power to detect an average expected difference of 10 minutes in time (5 min vs 15 min) to hemostasis (different primary outcomes compared to 6F study) between the SS and Perclose groups, using a two-sided alpha of 0.05. A standard deviation of 10 minutes is assumed, which will be the additional time for manual compression if any site oozing/bleeding is seen after the initial compression. A different standard deviation time was assumed given larger bore access for TAVR TFA access.

Descriptive summary statistics will be presented for all study variables. Continuous variables will be displayed as means with standard deviations and medians with 75th and 25th percentiles. Categorical variables will be summarized as frequencies with their respective percentages with two-sided 95% exact confidence intervals of the percentages. Statistical comparisons for continuous variables will be performed using the Student's t test or Mann-Whitney U test, as appropriate. Comparisons for categorical variables will be performed using the Chi square test or Fisher exact test, as appropriate. A two-sided P value of 0.05 will be considered statistically significant.

A single multivariate logistic regression will be reported for the safety outcome of hematoma formation. In order to create this model, study arm and variables known to place patients at higher risk for hematoma formation will be tested in univariate analysis for the primary safety outcome. Those variables with a P<0.10 will be included in backwards stepwise regression modeling to obtain a final model. Similar to our prior published study, the following variables will be analyzed: Age, sex, weight, hypertension, diabetes, creatinine, pre-procedural INR, pre-procedural platelet level, heparin dose given, PCI, last ACT prior to procedural end, and last SBP prior to procedural end.

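### The first hematoma check is set at Perclose deployment, before randomisation if read literally, and the safety outcome is not limited to hematomas that arise or grow after randomisation

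*Combined protocol and SAP*

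**What the plan says.** **Outcome.** Section III lists "Secondary outcome: The incidence of access hematomas". Section V makes hematoma the primary safety outcome, defined by size alone: "Hematoma formation: small ranging from small <5cm [I], 5-10cm [II] , or large >10cm".

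**Assessment schedule.** Sections III and V give the same list. Section V begins it: "Hematoma assessment will be done in multiple incidences: at the time of Perclose deployment while in the catheterization lab". Checks on admission to recovery and on inpatient admission follow, with repeated site checks in recovery and overnight up to 24 hours.

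**Randomisation.** Section IV (Timing of Subject Enrollment) has the patient "randomized at the conclusion of a successful deployment of the Perclose device", "at which time placement of the assigned device will occur". The envelope procedure agrees: "When a patient is officially enrolled (after Perclose™ deployment) the envelope corresponding to that patient number" is the one pulled and opened. The arm descriptions in Section IV (Protocol) likewise put the disc and the manual pressure after deployment.

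**Analysis.** Section VI states: "A single multivariate logistic regression will be reported for the safety outcome of hematoma formation". Its list of candidate variables does not include hematoma status at randomisation. The exclusion criteria and the baseline and procedural definitions do not mention an existing hematoma either.

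**The concern.** A randomised comparison of a safety event should count events that the assigned treatment could have caused or prevented. By the end of Perclose deployment the 14-16 Fr access and the valve procedure are over, so a hematoma from the puncture, the sheath or the deployment itself may already be there. If the check made at that moment is an outcome check, such a hematoma enters the outcome although neither arm's treatment had yet begun.

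The stake is dilution. Pre-existing cases add the same expected proportion to both arms and move the ratio toward 1. In a safety comparison that is the unhelpful direction: a real excess with the disc, or a real reduction, looks more like no difference. Hematoma is also the only outcome for which the plan specifies a regression model. Without a record made before allocation, the pre-existing cases may not be reliably separable afterwards.

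**Working it through.** **Order of events, from Sections III, IV and V**

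1. Perclose deployed; first listed hematoma check tied to this moment.
2. Deployment judged successful; envelope opened; arm assigned.
3. Disc applied (StatSeal arm) and manual pressure held (both arms), still in the catheterization laboratory.
4. Checks on admission to recovery, during recovery, on inpatient admission and overnight.

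No provision separates a hematoma found at step 1 from one that appears at steps 3-4.

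**The plan's own figure.** No rate, power or sample size is stated for hematoma. The only stated power, above 90% for time to hemostasis with 50 patients, reproduces: with a difference of 10 min, SD 10 min, 25 per arm and two-sided alpha 0.05, √(25/2) × 10/10 − 1.96 = 1.576, which gives 94.2% (93.4% by the t test). This point does not depend on it.

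**Inputs for the illustration, all assumed**

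- 25 patients per arm (50 is from Section VI; the allocation ratio is not stated, so 1:1 is assumed).
- New-hematoma rates of 30% (Perclose alone) and 10% (with StatSeal).
- A proportion q of patients, the same in both arms, with a hematoma before randomisation.
- Each patient counts once, as any hematoma or none.

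**Formula.** Observed rate = q + (1 − q)p, where p is the new-hematoma rate. The risk difference therefore shrinks by the factor (1 − q). For q = 10%: 0.10 + 0.90 × 0.30 = 37% and 0.10 + 0.90 × 0.10 = 19%; difference 18 points instead of 20; ratio 19/37 = 0.51.

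| q | Perclose alone | With StatSeal | Risk ratio | Exact Fisher power |
|---|---|---|---|---|
| 0 | 30.0% | 10.0% | 0.33 | 30.5% |
| 2% | 31.4% | 11.8% | 0.38 | 27.3% |
| 5% | 33.5% | 14.5% | 0.43 | 23.3% |
| 10% | 37.0% | 19.0% | 0.51 | 19.0% |
| 20% | 44.0% | 28.0% | 0.64 | 15.0% |

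With equal arms the calculation is symmetric. If the disc were the worse arm (30% vs 10%), power would be the same, and the ratio would fall from 3.0 to 37/19 = 1.95 at q = 10%.

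**False positives.** With a true new-hematoma rate of 10% in both arms, the exact type I error of the Fisher test at nominal 5% is 0.9% with q = 0, 1.8% at 5%, and 2.2% at 10% and at 20%. It stays below 5%.

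**Chance imbalance.** At q = 10% the between-arm difference in pre-existing hematomas has SD √(2 × 0.10 × 0.90/25) = 0.085, or 8.5 percentage points. This adds noise, which the test already allows for.

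**The case against.** **The timing phrase is loose.** The deployment check is the only one listed for the catheterization laboratory. Randomisation comes at the end of deployment, and at least five minutes of pressure follow in the same room. The phrase could mean the laboratory check around compression, which would be after assignment. That reading is reasonable and cannot be ruled out, so a reader should not infer that the plan certainly assesses hematoma before randomisation. But the plan does not say which is meant, and staff could time the check differently from patient to patient.

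**The outcome words suggest new events.** Incidence and formation ordinarily do. Neither section fixes a starting point, however, and both list the deployment check among the outcome's assessments. The case report forms are not in the text available, so a timed field may already exist.

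**Randomisation balances pre-existing cases.** It does so in expectation, and this stands. A reader might infer that uneven numbers of prevalent hematomas would bias the result or manufacture an effect. The type I error above does not support that. Dilution remains, because balance does not remove it.

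**The comparison is weak anyway.** The trial was sized for time to hemostasis, and no power is claimed for hematoma. With assumed rates of 10% vs 5%, Fisher power is 1-3% at every q from 0 to 20%. This also stands: redefining the outcome will not make the comparison well powered. It makes the estimate refer to the right events.

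**Adverse events are adjudicated for device connection (Section VII).** That helps identify unrelated hematomas in safety reporting, but it does not redefine the Section V outcome or the regression.

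**Conclusion.** The point holds as a gap in the outcome definition. The first hematoma check is tied to a moment that, read literally, precedes randomisation and disc placement, and nothing restricts the outcome to hematomas that arise or enlarge afterwards. The consequence is dilution toward no difference, not systematic bias and not excess false positives.

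Its size cannot be fixed from the documents. It depends on how often a hematoma is already visible at the end of a successful deployment, which they do not report. If that is rare, the loss is slight (about 3 percentage points of power at 2% in the illustration); at 10-20% it roughly halves an already low power. A reader might infer a large loss by assuming a stronger contrast: at 30% vs 4%, power falls from 60% to 25% at 20% pre-existing. Those rates have no source in the documents, and the same contrast loses little at 1-2% pre-existing (57% and 54%). No single power loss should be quoted as the effect of this gap.

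The change is worth making because it is cheap and because a baseline status that was not recorded is hard to reconstruct later.

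**What to change.** 1. Record hematoma presence and size immediately before the envelope is opened, and label that record baseline. This uses the check already scheduled at deployment.
2. In Sections III and V, define the safety outcome as a new hematoma, or an increase in size grade over baseline, from randomisation through the 24-hour checks. Use the same definition for the regression in Section VI.
3. Report baseline hematoma by arm.

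Every randomised patient stays in the assigned arm, so the intention-to-treat analysis is unaffected; only the start of the outcome period is fixed.

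The cost is one data field, a sentence in each of Sections III and V, and a slightly lower event count. No patients or visits are added. A baseline hematoma already in the largest grade cannot register growth, so any such patient should be visible in the baseline table.

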### **VI. STUDY STATISTICAL PLAN:**

This is a physician initiated, prospective, randomized, two-arm study, to be conducted at high-

volume academically affiliated centers with the cath lab staff having a (minimum) ten case experience using StatSeal Advanced. The primary analysis will be by intention-to-treat methodology.

A sample size of 50 patients is sufficient to have >90% power to detect an average expected difference of 10 minutes in time (5 min vs 15 min) to hemostasis (different primary outcomes compared to 6F study) between the SS and Perclose groups, using a two-sided alpha of 0.05. A standard deviation of 10 minutes is assumed, which will be the additional time for manual compression if any site oozing/bleeding is seen after the initial compression. A different standard deviation time was assumed given larger bore access for TAVR TFA access.

Descriptive summary statistics will be presented for all study variables. Continuous variables will be displayed as means with standard deviations and medians with 75th and 25th percentiles. Categorical variables will be summarized as frequencies with their respective percentages with two-sided 95% exact confidence intervals of the percentages. Statistical comparisons for continuous variables will be performed using the Student's t test or Mann-Whitney U test, as appropriate. Comparisons for categorical variables will be performed using the Chi square test or Fisher exact test, as appropriate. A two-sided P value of 0.05 will be considered statistically significant.

A single multivariate logistic regression will be reported for the safety outcome of hematoma formation. In order to create this model, study arm and variables known to place patients at higher risk for hematoma formation will be tested in univariate analysis for the primary safety outcome. Those variables with a P<0.10 will be included in backwards stepwise regression modeling to obtain a final model. Similar to our prior published study, the following variables will be analyzed: Age, sex, weight, hypertension, diabetes, creatinine, pre-procedural INR, pre-procedural platelet level, heparin dose given, PCI, last ACT prior to procedural end, and last SBP prior to procedural end.

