## **APPENDICES**

## I. INTRODUCTION, BACKGROUND & RATIONALE

Invasive cardiac catheterization-based procedures are done via transradial (TRA) or transfemoral access (TFA). These procedures are important in the diagnosis and treatment of coronary artery disease. Transradial access (TRA) for invasive cardiac catheterization procedures has gained significant popularity around the world compared with the transfemoral access. And in fact, and as early as 2016, the European Society of Cardiology guidelines have given transradial access its highest recommendation (Class I A) over femoral access. The most compelling reason for adopting TRA is the increased patient safety that results from the potential elimination of access site bleeding and vascular complications. In addition, TRA is associated with early sheath removal, improved patient comfort, faster recovery, and lower costs in comparison with transfemoral access.

One of the largest concerns of TRA vs TFA, is the occurrence of radial artery occlusion, which is in part related in part to prolonged radial artery compression time with such devices as the trans-radial air-bladder bracelet (TR band [TRB] (Terumo, Tokyo, Japan). Given that safe reduction in compressions times may reduce the risk of radial artery occlusion, we have previously shown that the adjunctive use of a potassium ferrate hemostatic patch (PFHP, Statseal Advanced RAD, Biolife, Sarasota, FL) with a TRB reduces composite overall complications and time to TRB deflation (68±15 vs 138 ± 62 min, P<0.001) as compared to use of the TRB alone. The PFHP contains potassium ferrate on a bed of hydrophilic polymer. The polymer rapidly dehydrates and concentrates blood solids, while the potassium ferrate agglomerates the solids & proteins together, forming a seal to the wound to stop bleeding. Beneath the seal, blood solids and proteins continue to concentrate and stack down, promoting hemostasis at the arteriotomy site without components of the PFHP reaching the vessel.

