### **IV. STUDY DESIGN AND METHODOLOGY**

#### **STUDY DESIGN**

This study is a physician initiated, prospective, observational, two arm, randomized study to be performed at one academically affiliated with high catheterization volumes. Enrollment will continue at each site on discretion of the investigators until at least 50 patients are enrolled. Clinicians will perform the catheterization in accordance with local standard practice, with no minimum amount of anticoagulation required during the procedure.

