#### Primary Efficacy Outcome:

- Total Time to Hemostasis (TTH), defined as from the time of manual compression after Perclose™ deployed until no further bleeding..

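### Any t test used for time to hemostasis should be Welch's rather than Student's pooled-variance test, because unequal spread is likely and equal arm sizes are not secured; the gain is small if the arms end near 25:25.

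*Combined protocol and SAP*

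**What the plan says.** The primary efficacy outcome (Section V) is "Total Time to Hemostasis (TTH), defined as from the time of manual compression after Perclose™ deployed until no further bleeding". Section VI gives one general sentence on testing it: "Statistical comparisons for continuous variables will be performed using the Student's t test or Mann-Whitney U test, as appropriate". It names no unequal-variance form of the t test and gives no rule for choosing between the two tests. The only confidence intervals it plans are for percentages.

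The sample size in Section VI rests on an "average expected difference of 10 minutes in time (5 min vs 15 min) to hemostasis", with one SD for both arms: "A standard deviation of 10 minutes is assumed". It explains that SD as added manual compression when oozing or bleeding is seen after the initial compression.

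In Section IV, the control and StatSeal procedures both require at least 5 minutes of manual pressure, starting at time zero. Randomization uses sealed envelopes in blocks of 25. No allocation ratio is stated, and on balance the text says only: "Device designation in the envelopes will be random in occurrence". Enrollment runs "until at least 50 patients are enrolled".

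The StatSeal timing data in the document are in Section I, for the radial band: "time to TRB deflation (68±15 vs 138 ± 62 min, P<0.001" in PCI patients, and 66 ± 14 v 113 ± 56 minutes for time to complete deflation.

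**The concern.** Student's t test assumes the same SD in both arms. When the SDs differ, its standard error is right only if the arms are equal in size. If the more variable arm is the smaller one, the standard error is too small and a nominal 5% test rejects too often. If the more variable arm is the larger one, the test is conservative.

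Three things in the document suggest that control will be the more variable arm:

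- **The floor.** If TTH includes the required 5 minutes of pressure, no value can fall below 5. An arm whose mean is 5 then has almost no spread, while an arm with mean 15 can have a good deal.
- **The source of the spread.** Section VI attributes it to extra compression for oozing, and Section I lists less oozing among the hoped-for benefits of adding the patch.
- **The earlier StatSeal data.** The control SD was about four times the StatSeal SD, though for another endpoint and access site.

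A block of 25 is odd, so no complete block can split evenly, and the last block may be incomplete because enrollment is open-ended. What is at stake is the calibration of the P value for the primary comparison, should a t test be chosen.

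**Working it through.** **1. The plan's power figure.** Inputs from Section VI: difference 10, SD 10, total 50, two-sided alpha 0.05. Assumed: 25 per arm. Noncentrality = 10 / (10 × √(1/25 + 1/25)) = 3.54 on 48 degrees of freedom, which gives power 0.934. The normal approximation gives 0.942. The claim of more than 90% reproduces.

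**2. SD ratios in Section I.** 62/15 = 4.13 and 56/14 = 4.0. A ratio of 4 is used below, with 2 as a milder case.

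**3. Standard error, pooled against true.** Take SDs of 4 (control) and 1 (StatSeal). Only the ratio matters.

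- Pooled variance = [(nC − 1) × 16 + (nS − 1) × 1] / 48
- Pooled SE² = pooled variance × (1/nC + 1/nS)
- True SE² = 16/nC + 1/nS

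Results:

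- 25:25: pooled variance 408/48 = 8.5; SE² 0.680 against 0.680; SE ratio 1.00.
- 24 control:26 StatSeal: 393/48 = 8.19; 0.656 against 0.705; SE ratio 0.965.
- 20 control:30 StatSeal: 333/48 = 6.94; 0.578 against 0.833; SE ratio 0.83.
- 30 control:20 StatSeal: SE ratio 1.20.

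**4. Real error of the nominal 5% test.** Simulation with equal means and total 50. Normal data: 400,000 runs per split at 4:1 and 200,000 at 2:1. Skewed data (shifted exponential, SDs 10 and 2.5, an assumption): 200,000 runs.

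| Control : StatSeal | Student, normal 4:1 | Student, normal 2:1 | Welch, normal 4:1 | Student, skewed 4:1 | Welch, skewed 4:1 |
|---|---|---|---|---|---|
| 20:30 | 10.7% | 8.4% | 5.0% | 12.8% | 7.7% |
| 22:28 | 8.3% | 7.0% | 5.0% | 10.4% | 7.5% |
| 24:26 | 6.2% | 5.7% | 4.9% | 8.5% | 7.3% |
| 25:25 | 5.5% | 5.2% | 5.0% | 7.6% | 7.2% |
| 26:24 | 4.6% | 4.6% | 5.0% | 6.7% | 7.1% |
| 28:22 | 3.3% | 3.7% | 5.0% | 5.2% | 6.8% |
| 30:20 | 2.2% | 2.8% | 5.0% | 4.0% | 6.7% |

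A repeat of the normal 4:1 case with 200,000 runs gave 6.3% at 24:26 and 10.9% at 20:30, so the last digit is simulation noise. With equal SDs, Student's test held about 5.0% at every split.

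**5. How likely is the imbalance?** If two blocks each split 12/13, the arms are 24 to 26. If the envelopes follow no fixed split, the control count is binomial (50, 0.5): P(22 or fewer) = 0.24 and P(20 or fewer) = 0.10. Averaged over all splits under that scheme, Student's error at 4:1 is about 6%.

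**6. Cost of Welch's test.** At SD 10 in both arms and 25:25, power is 93.4% with either test.

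**The case against.** The strongest reply is that a pooled t test is not fixed as the primary test. Mann-Whitney is an open alternative, and a floored, right-skewed outcome may well lead to it. That is correct, so the point applies only when a t test is used. Mann-Whitney is not immune to unequal spread either: with normal data, equal centers and a 4:1 ratio, its error was 7.2% at 25:25 and 10.5% at 20 control:30 StatSeal.

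Second, a reader might infer that the protocol's data show a fourfold SD ratio for TTH. They do not. Those SDs are for radial band deflation, and Section VI assumes a single SD of 10 for femoral TTH. The floor and the oozing argument support the direction of the inequality, not its size.

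Third, the large errors need a distinctly smaller control arm. The plan does specify blocks, and near-even blocks keep the error close to nominal.

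Fourth, if StatSeal had no effect at all and the two distributions were identical, the SDs would be equal and pooling would do no harm. The inflation concerns equal means with unequal spread. A mechanism that reduces oozing would probably lower both mean and spread, which makes that case less likely. At 5 v 15 minutes with SDs 2.5 and 10, power is at least 98.6% with either test for every split from 20:30 to 30:20, so the conclusion would rarely change.

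All four stand, and they limit the size of the point. They give no reason to prefer the pooled form in advance.

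**Conclusion.** The point holds as an inexpensive improvement of modest size. With normal data and a 4:1 SD ratio, the pooled test's error is about 4.6% to 6.3% when the arms end at 24 to 26. It rises to about 8% at 28 StatSeal:22 control and 11% at 30:20, which is a realistic prospect only if allocation is effectively simple randomization. When control is the larger arm, the test is conservative instead.

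Three stronger readings are not supported:

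- That the primary P value will be wrong. This depends on the test chosen, the SD ratio and the final split, and the documents settle none of them.
- That a planned confidence interval is miscalibrated. Section VI plans no interval for the TTH difference.
- That Welch's test is right in every case. On the skewed data its error was about 7% to 8%. It was still better than the pooled test when control was the smaller arm (7.5% v 10.4% at 22 control:28 StatSeal), but the pooled test was nearer nominal when control was the larger (5.2% v 6.8% at 28:22).

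The plan's power statement is unaffected.

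**What to change.** In Section VI, state that whenever a t test is used for TTH it will be Welch's unequal-variance t test in place of Student's. Add that the mean difference in TTH will be reported with its Welch 95% CI, which the plan does not currently provide. The Mann-Whitney option can stay as written for this purpose.

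The cost is a change of test name and one added sentence. It needs no extra data or patients, and power at the planned inputs is unchanged.
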